7.3 Safety, Disease Progression, and Survival Follow-Up Period Schedule

Patients may voluntarily discontinue study treatment for any reason at any time. If a patient decides to discontinue study treatment, the Investigator should make every effort to determine the primary reason for this decision and record this information in the patient's chart and on the appropriate eCRF pages. Reasons for discontinuation of study treatment are outlined in [Section 6.16](#).

At the time a patient discontinues study treatment, a visit should be scheduled as soon as possible, within 14 days of the last dose of study drug or within 14 days of the decision to permanently discontinue study treatment. If the decision to withdraw the patient occurs at a regularly scheduled visit, that visit may become the EOT visit.

Safety Follow-Up Period: Information related to all AEs (including concomitant medication taken for ongoing AEs) and SAEs will be collected for 30 days after the last dose of study drug. All AEs suspected to be related to study treatment and all SAEs should be followed up QW or as clinically indicated until resolution or stabilization. If a patient initiates subsequent systemic anti-cancer therapy, the patient will transition from Safety Follow-Up to Survival Follow-Up. Treatment-related SAEs should be reported, even if Safety Follow-Up has been completed.

Disease Progression Follow-Up Period: Patients who discontinue study treatment for any reason other than death, unequivocal disease progression, lost to follow-up, withdrawal of consent, start of new cancer therapy or study termination, should continue tumor evaluation assessments until progression of disease per RECIST v.1.1. If patients refuse to return for these visits or are unable to do so, every effort should be made to contact them, or a knowledgeable informant, by telephone to determine if the patient had disease progression. If a patient starts a new anti-cancer therapy during this period, Disease Progression Follow-Up will cease.

Survival Follow-Up Period: Patients will be followed for survival every 3 months (may be done by telephone call) until death or until the end of the study is reached, unless they withdraw consent or are lost to follow-up. For patients whose status is unclear because they fail to appear for study visits without stating an intention to withdraw consent, the Investigator should show "due diligence" by contacting the patient, family, or family physician as agreed in the informed consent. The Investigator should record in the source documents the steps taken to contact the patient, eg, dates of telephone calls, registered letters, etc. A patient should not be considered lost to follow-up until due diligence has been completed. Patients lost to follow-up should be recorded as such on the appropriate Patient Disposition eCRF.

Assessments required as part of the study are presented by visit in [Table 7-3](#). A visit window of ± 14 days is allowed during follow-up.

Table 7-3: Schedule of Follow-Up Assessments

Procedure	EOT	30 days post last dose	90 days post last dose then Q3M
All Patients			
Survival contact		X	X
Subsequent anti-cancer treatment	X	X	X
Patients in Safety Follow-Up			
Adverse events	X	X	
Concomitant medications	X	X	
Abbreviated physical examination	X	X	
Weight	X	X	
Vital signs	X	X	
12-lead ECG (single)	X	Only if abnormal at EOT	
ECOG performance status	X	X	
Hematology panel	X	X	
Chemistry panel	X	X	
Coagulation	X	Only if abnormal at EOT	
Urinalysis	X	Only if abnormal at EOT	
Thyroid function	X	Only if abnormal at EOT	
Pregnancy test (serum or urine, women of childbearing potential)	X	X	
Immunogenicity	X		
Patients in Disease Progression Follow-Up			
CT/MRI scans and disease assessment	Q8W to Week 40 (post C1D1) then Q12W		
Tumor biopsy (optional)	Recommended at time of progression		

CT = computed tomography; ECG = electrocardiogram; ECOG = Eastern Cooperative Oncology Group; EOT = End of Treatment; MRI = magnetic resonance imaging; PK = pharmacokinetics; Q3M = every 3 months.

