8.2 Adverse Events

All AEs regardless of study drug relationship will either be collected from the signing of consent up to the end of the 30 day follow-up based on current protocol versions 3.0 and 4.0 or 90 day follow up based on the previous protocol versions. Those AEs with onset 31-90 days after the last dose will be flagged in the separate adverse events listing.

- 1) Treatment-emergent adverse events (TEAEs) are defined as any adverse event after the first dose of study drug within 30 days of the last dose of study drug or prior to subsequent anti-cancer therapy, whichever is sooner. For adverse events on C1D1, the event onset time relative to the first dose time will be considered (if relative or actual times are available), otherwise AE starting on C1D1 will be assumed treatment-emergent.

The AE summary tables include only AEs that are new or worsened during the on-treatment period (TEAEs). However, all safety data (including those from the pre- and post-treatment periods) will be listed and those collected during the pre-treatment and post-treatment period are to be flagged.

The incidence of TEAEs will be summarized by system organ class (SOC) and/or PT, severity (based on NCI CTCAE v.4.03 grades), and relation to study treatment by treatment group (as defined in Section 4.2.1). Serious TEAEs resulting in death and non-fatal serious TEAEs will be listed by patient and tabulated by treatment group. There will be a separate listing for TEAE leading to treatment discontinuation.

AEs will be coded by MedDRA version 20.0.

For the purpose of inclusion in TEAE tables, incomplete AE onset and end dates will be imputed as follows:

- Missing onset dates (where UK and UKN indicate unknown or missing day and month respectively):
 - UK-MMM-YYYY: If the month and year are different from the month and year of the first dose of study drug, assume 01-MMM-YYYY. If the month and year are the same as the first dose of study drug month and year, and the end date (after any imputation) is on or after the first dose of study drug, then assume the date of the first dose of study drug. If the month and year are the same as the first dose of study drug month, and year and the end date (after any imputation) is prior to the first dose of study drug, then assume the end date for the onset date.

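### The plus or minus 14-day window on the 30-day safety visit lets the last scheduled AE enquiry fall on Day 16, leaving up to 14 of the 30 post-treatment days without one

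*Protocol*

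**What the plan says.** Protocol Section 7.3 sets the collection period: AEs and "SAEs will be collected for 30 days after the last dose of study drug". SAP Section 8.2 uses the same horizon for TEAEs, counting those with onset "within 30 days of the last dose of study drug or prior to subsequent anti-cancer therapy, whichever is sooner".

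Table 7-3 has three follow-up columns: EOT, "30 days post last dose", and 90 days then every 3 months. The AE row is marked in the first two and blank in the third. The sentence introducing the table gives a single window for all of them, plus or minus "14 days is allowed during follow-up".

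Section 7.3 places the EOT visit "within 14 days of the last dose of study drug or within 14 days of the decision to permanently discontinue study treatment". AEs suspected to be related, and all SAEs, "should be followed up QW or as clinically indicated until resolution or stabilization". A patient who starts new systemic anti-cancer therapy leaves Safety Follow-Up for Survival Follow-Up. Treatment-related SAEs stay reportable after Safety Follow-Up ends.

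**The concern.** The collection period and the visit meant to close it do not match. A site that holds the 30-day visit on Day 16 complies with the protocol, and from then on nothing in the schedule prompts anyone to ask about Days 17 to 30. No section requires an AE contact on or after Day 30.

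The incidence and severity of AEs and SAEs is listed among the Phase I primary endpoints and the Phase II secondary endpoints (protocol Table 4-1; SAP Sections 3.2.1 and 3.2.2). SAP Section 8.2.1 reports TEAEs as the percentage of safety-set patients with at least one event. A patient last asked on Day 16 therefore enters the denominator exactly like one asked on Day 44. If events from unasked days are missed, the reported incidence can only move down.

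**Working it through.** The plan gives no derived figure on this point, so there is nothing to reproduce. The check is day arithmetic, with days counted from the last dose unless stated.

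**Inputs**
- Nominal visit day: 30 (Table 7-3).
- Window: 14 days either way (Section 7.3).
- Collection and TEAE period: 30 days (Section 7.3; SAP Section 8.2).
- Next contact scheduled for all patients: Day 90, with no AE row (Table 7-3).

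**Range of compliant visit days**
- Earliest: 30 − 14 = Day 16.
- Latest: 30 + 14 = Day 44.

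**Days with no scheduled AE enquiry**, for a visit on day d: max(0, 30 − d)
- d = 16: 14 days (Days 17 to 30), 14/30 = 47%.
- d = 23: 7 days, 7/30 = 23%.
- d = 30 or later: 0 days.

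Only the early side of the window causes the problem.

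**Next contact.** With its own window the 90-day contact falls between 90 − 14 = Day 76 and 90 + 14 = Day 104. That is 60 to 88 days after a Day 16 visit, and it covers survival and subsequent therapy only.

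**Does EOT fill the gap?** Timed from the last dose, EOT is due by Day 14, before Day 16. EOT on Day 14 and the 30-day visit on Day 16 would both comply: two enquiries two days apart, then none. Timed from the decision to stop, EOT may fall later and could land in Days 17 to 30, but this is not guaranteed.

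**Typical size.** The documents do not say when visits take place, so the loss per patient can be anywhere from 0 to 14 days. As an illustration only, assume visits spread evenly over the window. Half are then early and lose 14/2 = 7 days on average, or 3.5 days over all patients (3.5/30 = 12% of the post-treatment period).

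**Against the whole TEAE period.** The 47% is a share of the 30-day tail. For a patient given one full cycle on schedule, the last dose is on study Day 22 and the TEAE period ends on study Day 22 + 30 = 52; the worst case is 14/52 = 27%. After two full cycles the last dose is on study Day 28 + 22 = 50, the period ends on study Day 80, and the worst case is 14/80 = 17.5%. The share falls further with longer treatment.

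**DLT check.** Under protocol Section 6.10.2 a patient counts as DLT-free only with at least 3 doses and at least 28 days of observation from the first dose. With at least 7 days between doses (Section 7.2), the third dose cannot come before study Day 15. The earliest 30-day visit is then study Day 15 + 16 = 31, after the DLT period has closed.

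**The case against.** The strongest reply is that a visit window does not cancel a collection duty. That is right. Section 7.3 still requires collection for 30 days, and Section 8.6 makes the investigator responsible for it. A reader might infer that the protocol shortens AE collection to 16 days or contradicts itself. It does neither. What is missing is a scheduled contact to support the duty.

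A reader might also infer that late events are recorded only if the patient volunteers them. The documents do not support that in general:
- Patients whose treatment is stopped for an AE or a clinically significant laboratory value are followed at least weekly for 4 weeks (Section 6.15.2).
- Known related AEs and all SAEs are followed weekly or as clinically indicated, and EOT may itself fall after Day 16 (Section 7.3).
- Patients who start new anti-cancer therapy leave the TEAE window at that point (SAP Section 8.2).

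These provisions narrow the affected group. They do not cover new-onset events in a patient who stopped, say, for progression and was seen early.

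Because AE incidence is a Phase I primary endpoint, it is tempting to conclude that the dose decision is at risk. It is not. The MTD rests on DLTs, and no patient counted as DLT-free depends on the early side of this window.

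Finally, the protocol gives reasons to expect few drug-related events this late: a half-life under 24 hours, and onset of related events expected within 24 hours of a dose. That limits the likely number of missed related events. It does not remove the point, because the TEAE tables count all events whatever their cause, and the protocol itself chose 30 days.

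**Conclusion.** The gap is real but limited. A compliant schedule can leave up to 14 of the 30 post-treatment days without a scheduled AE enquiry. This is a worst case; no average can be derived from the documents.

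It mainly affects new-onset events in patients who meet three conditions: they stopped for a reason other than an AE or laboratory value, they were seen before Day 30, and they had not started new anti-cancer therapy. For them the descriptive TEAE and SAE incidence may be biased downward by an amount that cannot be estimated from the plan. The study is uncontrolled and tests no hypotheses (SAP Section 4), so no formal inference is affected, and neither is the DLT-based choice of dose. The change is worth making because it is cheap, not because the trial's conclusions depend on it.

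**What to change.** In protocol Section 7.3 and Table 7-3, do one of the following:
- give the 30-day safety visit its own window of 0/+14 days (Days 30 to 44), which leaves no uncovered days; or
- keep the present window and require an AE enquiry, by telephone if convenient, on or after Day 30 before Safety Follow-Up is closed.

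Exempt patients who have already moved to Survival Follow-Up on starting new systemic anti-cancer therapy. Keep plus or minus 14 days for survival contacts. SAP Section 8.2 needs no change.

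The cost is a line of text and either slightly less scheduling freedom or one telephone call for each patient seen early.

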7.4 Details of Assessments

Details for the collection, processing, storage and shipment of all samples are provided in the laboratory manual along with the order of prioritization for sampling, where sampling time points are scheduled to occur at the same time. Blood samples scheduled at the same time point should be taken after the ECGs have been completed. Any remaining [REDACTED] samples may be kept for up to 15 years after the end of the study for additional testing to understand the cancer, the drug response, or to validate diagnostic [REDACTED] assays.

7.4.1 HLA-A*02:01 and NY-ESO-1 / LAGE-1A Testing

A 2 mL blood sample will be taken and sent to the central laboratory for DNA extraction and determination of HLA-A*02:01 status using a sequence-based assay for HLA-A*02:01. Any remaining DNA sample will be kept up to 15 years in case additional testing is required.

If the patient is already known to be HLA-A*02:01 positive, the HLA sample and tumor sample can be submitted in parallel, otherwise patients must have HLA-A*02:01 tested centrally and be confirmed as positive prior to tumor samples being sent for NY-ESO-1 and LAGE-1A expression testing.

Patients confirmed as HLA-A*02:01 positive will submit a tumor sample for NY-ESO-1 and LAGE-1A expression testing. This can be an archival or fresh sample. NY-ESO-1 and LAGE-1A antigen positivity will be confirmed using a quantitative, real-time, reverse transcription polymerase chain reaction (qRT-PCR) assay that tests in parallel for NY-ESO-1 and LAGE-1A expression levels.

Further background regarding the NY-ESO-1 / LAGE-1A screening strategy is provided in [Section 1.5](#).

7.4.2 Patient Demographics and Other Baseline Characteristics

Data to be collected will include general patient demographics, relevant medical history and current medical conditions, diagnosis and extent of cancer, details of prior anti-cancer treatments (including systemic therapy, radiotherapy, and surgery), prior/concomitant medications, prior procedures, significant non-drug therapies and any other assessments done for determining eligibility for inclusion in the study.

7.4.3 Efficacy Assessments

Tumor response will be determined locally according to (RECIST) v.1.1. Further details about RECIST v1.1 are in [Section 13.1](#). Patients may receive treatment after disease progression per RECIST v1.1 based on criteria in [Section 6.18](#).

During the study, Immunocore may decide to have a central review of the radiological assessments performed. In such case, the Investigator's staff will be instructed on how to send data from these radiological assessments to the Contract Research Organization (CRO) for central review when needed.

The Sponsor reserves the right to request additional scans obtained within 6 months of the screening assessment to evaluate tumor growth kinetics prior to and following treatment with IMCnyeso.

See [Table 7-4](#) for details regarding disease assessments. If a patient is intolerant of iodine-based contrast agents, CT may be performed without contrast. Visible skin lesions and easily palpable subcutaneous tumors may be measured by physical examination using a ruler or calipers. Ultrasound should not be used to measure sites of disease.

Table 7-4: Disease Assessment Collection Plan

Procedure	Screening/Baseline	During Treatment / Follow-up
CT or MRI with contrast enhancement (chest and abdomen; also, pelvis as appropriate based on indication and extent of disease)	Mandatory	Mandatory The same imaging modality should be used throughout the study (CT or MRI)
Brain MRI with contrast	Required only if clinical suspicion of brain metastasis at Screening	If disease was detected at Baseline or if clinically indicated

CT = computed tomography scan; MRI = magnetic resonance imaging.

7.4.4 Safety and Tolerability Assessments

Safety will be monitored by performing physical examination, and evaluating vital signs, ECG, weight, performance status, hematology, chemistry, coagulation, urinalysis, thyroid function, cytokine testing, and collection of AEs. Significant findings present at Screening must be included in the Medical History eCRF page. Significant new findings that begin or worsen after the start of Screening must be recorded as AEs in eCRF.

A complete physical examination will include the examination of general appearance, skin, neck (including thyroid), eyes, ears, nose, throat, lungs, heart, abdomen, back, lymph nodes, extremities, and neurological system. If indicated based on medical history and/or symptoms, rectal, external genitalia, breast, and pelvic exams will be performed. An abbreviated physical examination will include the examination of general appearance and body sites as directed by signs and symptoms.

Vital signs include body temperature, pulse, respiratory rate, and blood pressure. Additionally, blood oxygen saturation should be included in vital sign assessments at Screening and for at least the first 3 treatment cycles. Vital signs should be assessed on the scheduled day, even if study treatment is being withheld. More frequent examinations may be performed, at the discretion of the Investigator, if medically indicated and should be recorded as unscheduled assessments in the eCRF.

Height will be measured in cm and body weight to the nearest 0.1 kg in indoor clothing.

A standard 12-lead ECG will be performed (in triplicate at Screening and once at other timepoints). To ensure the safety of the patients, a qualified individual at the Investigator Site will review the ECG measurements. New or worsening clinically significant ECG findings occurring after informed consent should be confirmed by performing at least 2 additional ECG reads within approximately 30 minutes and taking the average of at least 3 manually over-read measurements. Confirmed new or worsening clinically significant ECG abnormalities must be reported as AEs in the eCRF.

Eastern Cooperative Oncology Group (ECOG) performance status is determined as indicated in [Table 7-5](#).

Table 7-5: ECOG Performance Status

Grade	Eastern Cooperative Oncology Group Status
0	Fully active, able to carry on all pre-disease performance without restriction
1	Restricted in physically strenuous activity, but ambulatory and able to carry out work of a light or sedentary nature (eg, light housework, office work)
2	Ambulatory and capable of all self-care, but unable to carry out any work activities. Up and about more than 50% of waking hours
3	Capable of only limited self-care. Confined to bed or chair more than 50% of waking hours
4	Completely disabled. Cannot carry on any self-care. Totally confined to bed or chair
5	Death

Laboratory parameters assessed for safety purposes, shown in [Table 7-6](#) will be evaluated locally. Normal ranges and accreditation documentation must be provided for all local laboratories. More frequent evaluations may be performed if medically indicated; results should be recorded as unscheduled laboratory assessments in the eCRF.

Table 7-6: Local Clinical Laboratory Parameters Collection Plan

Test Category	Test Name
Hematology	Hemoglobin, platelets, white blood cells, lymphocytes, and neutrophils
Chemistry	Albumin, alkaline phosphatase, alanine transaminase, aspartate transaminase, bicarbonate, calcium, chloride, creatinine, glucose, magnesium, inorganic phosphate, potassium, sodium, total bilirubin (also measure direct and/or indirect bilirubin if total bilirubin is $> 1.5 \times \text{ULN}$), blood urea nitrogen or urea, amylase, and lipase
Coagulation	Prothrombin time or international normalized ratio and activated partial thromboplastin time
Urinalysis	Bilirubin, blood, glucose, ketones, pH, protein, specific gravity and white blood cells (in the event of macroscopic findings, microscopy may be performed at the Investigator's discretion)
Thyroid	Free T4 and thyroid stimulating hormone (also measure free T3 if TSH is suppressed but free T4 is normal)
Pregnancy / menopausal status	hCG (women of childbearing potential) FSH (if required to confirm non-childbearing potential)

hCG = human chorionic gonadotropin; FSH = follicle-stimulating hormone; T3 = triiodothyroxine; T4 = thyroxine; TSH = thyroid stimulating hormone.

Pregnancy tests will be performed for all women of childbearing potential. Any pregnancy must be reported as described in [Section 8.5.6](#), and the patient should be withdrawn from treatment. For post-menopausal patients, FSH at Screening must be within the laboratory's post-menopausal reference range.

7.4.5 Pharmacokinetics and Immunogenicity Assessments

Blood samples (2 mL) will be taken for IMCnyeso PK analysis. At C1D1 and C1D8, a full PK profile sampling schedule is specified, assuming hospitalization of the patient for these doses and "out-patient" sampling at doses 3 and 4 (C1D15 and C1D22). To generate C_{\min} data only, subsequent sampling is limited to pre-dose and EOT. It is essential that the actual time and date of sample collection is recorded on the patient's eCRF.

A 2-mL blood sample will also be taken to measure IMCnyeso anti-drug antibody (ADA) levels.

[REDACTED]

[REDACTED]

[REDACTED]

A large black rectangular redaction box covers the majority of the page content, starting below the header and ending above the footer. The redaction is not perfectly uniform, with some white space visible at the top and bottom edges.

7.4.6.3 Skin Punch Biopsy

An OPTIONAL skin punch biopsy (3 mm or 5 mm, depending on the size of the area affected) is to be taken in patients experiencing \geq Grade 3 rash, to characterize immune activation status in the skin and potentially identify the mechanisms of skin toxicity.

8 ADVERSE EVENTS AND SAFETY REPORTING

8.1 Assessment of Safety

Timely, accurate and complete reporting and analysis of safety information from clinical studies are crucial for the protection of patients and is mandated by regulatory agencies worldwide. The Sponsor and CRO have established standard operating procedures in conformity with regulatory requirements worldwide to ensure appropriate reporting of all safety information. All clinical studies conducted by the Sponsor or its affiliates will be conducted in accordance with those procedures.

Individual AEs should be evaluated by the Investigator and should be reported to the CRO/Sponsor for evaluation. This includes the evaluation of the event's seriousness and the causality between the study drug and/or concomitant therapy and the AE. The CRO/Sponsor is required to maintain detailed records of all AEs reported by the Investigator(s) and to perform an evaluation with respect to seriousness, causality, and expectedness. On request of a competent authority in whose territory the clinical trial is being conducted, the Sponsor should submit detailed records of all AEs that are reported by the relevant Investigators. Case report processing includes evaluation of data in individual cases, identification of individual cases requiring specific handling, recognition and processing of alerts, and any other data processing of aggregated cases.

